significant progressive disease or intolerable toxicity) may receive repeated cycles of SL-401 even if eradication of MRD, in the judgment of the Investigator, is not attained. Patients can receive up to 6 total cycles of SL-401 as long as there is evidence of ongoing AML remission, according to their physician Investigator. The administration of additional cycles of SL-401 (> 6 cycles) must be discussed with the Medical Monitor at which time the individual patient's potential risk/benefit of further treatment will be assessed.

Patients will receive the following premedications approximately 60 minutes before each SL-401 infusion:

- Acetaminophen 650 mg by mouth (PO)
- Diphenhydramine 50 mg IV
- Methylprednisolone 50 mg IV (or an equivalent dose of another corticosteroid)
- Ranitidine 50 mg IV (or an equivalent dosage of another H₂-histamine antagonist)

During the dosing period for each cycle, individual SL-401 infusions may be delayed to allow for toxicity resolution, as detailed in Section [7.5.5](#).

Concomitant Medications:

Recommended Medications Per Institutional Guidelines/Practices:

Patients may receive the following types of prophylactic therapies/regimens, if indicated by institutional guidelines/practices:

- Antibacterial: ciprofloxacin, levofloxacin, or an equivalent antibiotic
- Antifungal: fluconazole, voriconazole, or an equivalent antifungal
- Antiviral: acyclovir, valacyclovir or an equivalent antiviral

Allowed Medications/Therapies:

All patients may receive supportive care measures as clinically indicated, including prophylactic antibiotics, antihistamines, antiemetics, albumin, fluids (hydration), and supportive measures. Patients may receive growth factor support and/or blood product transfusions as per the discretion of their physician.

Albumin 25 g IV daily should be administered if serum albumin is <3.0 g/dL on days when treatment has been withheld or in the immediate post-treatment period. The Investigator has discretion with regard to frequency of administration.

Prohibited Medications/Therapies:

Prior to discontinuation of SL-401, patients may not receive investigational or non-investigational anticancer or anti-leukemia agents, including cytotoxic chemotherapy agents, hypomethylating agents (5-azacytidine, decitabine, and others), or anticancer tyrosine kinase inhibitors (including imatinib, ruxolitinib, sorafenib, and others) or therapeutic monoclonal antibodies.

Assessments:

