6.2.2 Stage 2: Expansion

During Stage 2, up to 20 additional patients with evidence of MRD as determined locally will be treated at the MTD or maximum tested dose at which multiple DLTs are not observed (identified in Stage 1) so that up to 15 patients with evidence of MRD as determined centrally are evaluable for safety and response at this dose. For inclusion in the study, all patients treated in the expansion phase should have MRD in bone marrow, as determined locally, via at least one of the following modalities: multi-parametric flow cytometry, cytogenetic evaluation, FISH, real-time PCR, or next-generation gene sequencing. It is anticipated that at approximately 50% of patients evaluated with AML in first remission (CR or CRi) will have evidence of MRD.

6.2.3 Tumor Assessments during Stages 1 and 2

All patients must have a baseline (pre-treatment) bone marrow aspirate (+ biopsy) and peripheral blood sample within 14 days prior to the first administration of SL-401. Subsequent assessments will be performed on the following schedules until, in the judgment of the Investigator, there is evidence of relapsed or progressive disease:

- Bone marrow aspirates (+ biopsy) and peripheral blood samples 28 (\pm 7) days after the start of Cycles 2, 4 and 6, then every 3 months (\pm 1 month) until Month 12. No repeat bone marrow is necessary if non-response or progressive disease can be unequivocally diagnosed from peripheral blood tests.
- If the Cycle 2 (Day 28 [\pm 7]) bone marrow examination is empty (i.e., hypocellular) or inadequate, a bone marrow examination should be repeated in 14 (\pm 7) days to document response. If additional time is required to complete the repeat examination, consult with the Medical Monitor.
- Bone marrow will be assessed for morphologic evidence of AML recurrence, and flow cytometric and other cytogenetic/molecular assessments, including evaluation of MRD.
- CD123 is to be assessed in all bone marrow samples (and, if applicable, tissue samples) by flow cytometry (i.e., CD123 should be added to the panel of markers assessed by flow cytometry of bone marrow aspirates) and immunohistochemistry and the results recorded and captured in the electronic case report form (eCRF). (The Cycle 2, 4, and 6, Day 28 [\pm 7 days] peripheral blood and bone marrow assessment should occur on Day 28 [\pm 7 days] even in the setting of patients receiving SL-401 over 6-10 days [as opposed to 5 consecutive days]).

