7.5.2 Dose, Schedule, and Duration of Treatment

Patients will receive SL-401 by IV infusion over 15 minutes for 5 consecutive days (or 5 doses over a period not to exceed 10 days if postponement is required for toxicity) of a 28-day cycle in the absence of disease progression or other withdrawal criteria.

Refer to the Pharmacy Manual for details regarding SL-401 administration.

Patients with evidence of ongoing disease control during treatment (without evidence of clinically significant progressive disease or intolerable toxicity) may receive repeated cycles of

SL-401 even if eradication of MRD, in the judgment of the Investigator, is not attained. Patients can receive up to 6 total cycles of SL-401 as long as there is ongoing evidence of AML remission, as determined by the Investigator. The administration of additional cycles of SL-401 (> 6 cycles) must be discussed with the Medical Monitor at which time the individual patient's potential risk/benefit of further treatment will be assessed.

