7.5.5.10.2 Hematological Toxicity

Patients with neutropenia or thrombocytopenia as a consequence of their disease do not require treatment interruptions for myelosuppression. Dose-modifications in these patients should be considered on a case-by-case basis and discussed with the Medical Monitor. The following guidelines can be used for these patients:

- Patients with a response and pre-cycle counts of neutrophils $>1000/\mu\text{L}$ and platelets $>50,000/\mu\text{L}$ who have sustained low counts of neutrophils $<500/\mu\text{L}$ and/or platelets $<20,000/\mu\text{L}$ for more than 2 consecutive weeks in the current cycle, may receive a subsequent cycle of SL-401 at a reduced dose, at the Investigator's discretion.
- If there are persistent blasts in the peripheral blood or $>5\%$ blasts in the bone marrow, continue treatment regardless of neutrophil and platelet count and give supportive care as needed.
- If no evidence of leukemia in the bone marrow, consider holding (postponing) therapy until recovery of neutrophils to $\geq 1000/\mu\text{L}$ and platelets $\geq 50,000/\mu\text{L}$, then resume SL-401 at the same or reduced dose according to guidelines mentioned above.

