7.6 Treatment Discontinuation

7.6.1 Criteria for Treatment Discontinuation

SL-401 treatment may be discontinued for any of the following reasons:

- Patient withdrawal of consent
- Occurrence of unacceptable toxicity, including DLT
- SL-401 related anaphylaxis or Grade ≥ 3 hypersensitivity reaction
- Requirement for > 1 dose reduction unless there is evidence of MRD eradication or sustained AML remission (beyond Cycle 2), in which case additional dose reductions are permitted, however, these reductions must be discussed with the Medical Monitor and documented in the context of ongoing AML response.
- Disease recurrence/progression
- Intercurrent illness that prevents further administration of SL-401
- Patient non-compliance
- Occurrence of pregnancy
- Completion of 6 cycles of treatment. (The administration of additional cycles of SL-401 [beyond 6 cycles] may be considered in the setting of MRD eradication, sustained AML remission, or other evidence of sustained anti-leukemia benefit in the opinion of the Investigator. Administration of SL-401 beyond 6 cycles must be discussed with the Medical Monitor at which time the individual patient's potential risk/benefit of further treatment will be assessed).

- Investigator's decision

The reason for SL-401 discontinuation and the date of discontinuation should be recorded in the eCRF.

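### Protocol 7.5.5.10.2 tells sites to continue SL-401 when blasts are present, and nothing makes that instruction subject to the ongoing-remission condition in 7.5.2 (minor)

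*Protocol*

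**What the plan says.** Section 7.5.5.10.2 opens by stating that disease-related neutropenia or thrombocytopenia does not oblige a site to interrupt treatment. Dose changes are left to individual decisions with the Medical Monitor. Three bullets follow, introduced by "The following guidelines can be used for these patients". The second covers patients with persistent blasts in the blood or more than 5% blasts in the marrow, and says to "continue treatment regardless of neutrophil and platelet count and give supportive care as needed".

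The conditions for giving SL-401 at all are elsewhere. Section 7.5.2 provides for dosing "in the absence of disease progression or other withdrawal criteria". It allows repeat cycles without clinically significant progression, up to 6 in total, "as long as there is ongoing evidence of AML remission, as determined by the Investigator". The synopsis repeats the remission condition: "as long as there is evidence of ongoing AML remission, according to their physician Investigator". Section 7.6.1 lists recurrence or progression among the grounds for stopping, under the lead-in "SL-401 treatment may be discontinued for any of the following reasons".

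Appendix A notes that all patients are in CR or CRi at entry. Both states require marrow blasts of 5% or less and no leukemic blasts in blood. Section 11.5.2 and Appendix A place relapse after CR/CRi at blasts above 5%. If there are no blood blasts, a confirmatory aspirate is needed at least 1 week later.

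**The concern.** An instruction to keep treating through low counts because blasts persist suits a trial in active leukemia. Here every patient starts in remission, so blasts seen on study would be a new finding and a possible relapse. The bullet attaches a direction to continue dosing to the same finding that should prompt a site to ask whether the patient may still be dosed.

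Two things are at stake. The first is consistency: for the same patient, one site could follow the bullet and give another cycle while another follows 7.5.2 and stops, each citing the protocol. The second is safety: a cytopenic patient in relapse could receive a further cycle, during which Section 7.4 bars other anti-leukemia therapy. The setting is plausible, because CRi is eligible and inclusion criterion 10 asks only for an ANC above 0.5 x 10^9/L, with no platelet minimum.

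**Working it through.** There is no figure to reproduce. The check sets the 5% blast threshold and the dosing conditions side by side.

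| Finding on study | Status under Appendix A and 11.5.2 | 7.5.2 and synopsis | 7.5.5.10.2, second bullet (cytopenic patient) |
|---|---|---|---|
| Marrow 5% or less, no blood blasts | Within the CR/CRi blast criteria | Cycles allowed | Not triggered |
| Marrow 5% or less, persistent blood blasts at or below 5% | Outside CR/CRi if the blasts are leukemic; below the relapse threshold | Depends on the Investigator's judgment of remission | Continue |
| Marrow above 5%, no blood blasts | At the relapse threshold, confirmation aspirate pending | Remission in doubt; not allowed once relapse is confirmed | Continue |
| Marrow above 5%, blood blasts present | Relapse | Not allowed if the Investigator applies these criteria | Continue |

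1. **The trigger falls outside remission as the protocol defines it.** Only the first row meets the CR/CRi blast criteria, and the bullet does not apply there. In the other three rows remission is lost or in question.
2. **The action differs.** In the last row the bullet says continue, whereas 7.5.2 and the synopsis no longer support a cycle. In the two middle rows the bullet gives an answer before the remission question has been settled. It neither asks for the confirmatory aspirate nor limits itself to the interval before one.
3. **The bullet is worded more firmly than its neighbors.** The first bullet permits a reduced dose at the Investigator's discretion and the third suggests considering a hold. The second simply says to continue.
4. **No text settles which section governs.** Section 7.5.5.10.2 does not refer to 7.5.2 or 7.6.1. The lead-in to 7.6.1 is permissive, so it does not override the bullet. The Medical Monitor discussion is tied to dose modifications, and continuing at an unchanged dose is not clearly one.

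**The case against.** The strongest reply is that the sections answer different questions. The bullet sits under hematological toxicity, after a sentence about interruptions for myelosuppression, so it may say only that low counts do not force a hold when leukemia explains them. Eligibility for another cycle would remain with 7.5.2, and a toxicity rule need not restate it. This reading is reasonable and may be what was intended. It softens the conflict but does not remove it, because the reader has to supply the link to 7.5.2.

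The trigger is also not the same as confirmed relapse. Blood blasts at or below 5% are not relapse, an isolated marrow finding needs confirmation, and 7.5.2 leaves remission to the Investigator without tying it to Appendix A. That stands. A reader might infer that no patient could ever satisfy both the trigger and 7.5.2; the text does not go that far.

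The bullets are guidelines, and Investigators could differ on the same patient even if this one were deleted. That also stands, although the bullet gives one of the two choices explicit support.

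Finally, SL-401 may help in relapse: Section 3.6.1 reports 2 CRs and 5 PRs in relapsed or refractory AML. Dosing in relapse therefore cannot be called harmful on these documents. But that study enrolled a different population, and the present protocol chose to make remission a condition of treatment.

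**Conclusion.** The concern holds as a minor defect of wording in a dosing guideline. Read literally, the second bullet directs further SL-401 in patients for whom 7.5.2 and the synopsis may no longer allow it, and nothing states which prevails. This rests on the CR/CRi and relapse criteria of Appendix A and 11.5.2 being the ones an Investigator would use to judge remission.

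The gain from correcting it is consistent dosing and patient safety only. The DLT rules, the MTD definition, the sample size and the error rates are untouched. How many patients would meet the trigger cannot be estimated; the visit calendar shows when blasts could be found, not how often.

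Three stronger conclusions might be inferred and are not supported:

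- *The third bullet contradicts the second.* It begins "If no evidence of leukemia in the bone marrow, consider holding (postponing) therapy until recovery of neutrophils" and covers patients without marrow leukemia. Considering a hold when leukemia does not explain the low counts, and not holding when it does, is coherent.
- *Patients dosed after relapse would have no scheduled marrow.* Section 6.2.3 does say "Subsequent assessments will be performed on the following schedules until, in the judgment of the Investigator, there is evidence of relapsed or progressive disease", but Section 9.4.6 and Table 6 schedule marrows at the end of Cycles 2, 4 and 6 with no relapse cut-off of their own.
- *A relapsed patient would be locked into SL-401 by Section 7.4.* That restriction ends when SL-401 is discontinued, and the Investigator may discontinue at any time.

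**What to change.** Delete the second bullet of Section 7.5.5.10.2, or replace it with: *Blasts in peripheral blood or >5% marrow blasts: assess for relapse per 11.5.2/Appendix A; further SL-401 only if 7.5.2 is still met, after discussion with the Medical Monitor.*

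The replacement keeps clinical discretion and makes clear that 7.5.2 governs. It costs one sentence in the protocol and needs no new data, no SAP change and no recalculation. SAP Section 3.1 already reports enrollment at database lock (18 patients in Stage 1 and 9 in Stage 2), and the documents do not show whether anyone is still on treatment. The edit would therefore serve mainly any such patient and any later protocol that reuses this text.

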7.5.5.11 Dose Reduction Schedule

Table 4 summarizes the potential reduced dose for a subsequent cycle relative to the starting dose or dose for a prior cycle. The reason(s) for all dose modifications must be recorded in the eCRF.

Table 4: Reduced Dose Relative to Dose in Prior Cycle

Dose for a Given Cycle	Reduced Dose for Subsequent Cycle
12 µg/kg/day	9 µg/kg/day
9 µg/kg/day	7 µg/kg/day
7 µg/kg/day	5 µg/kg/day

Dose changes should only occur once a cycle has been completed. Intra-cycle dose modifications will not be permitted. Potential dose modifications will be based on the severity and resolution of toxicities. Once the dose has been reduced a subsequent increase is not permitted. Cases requiring >1 dose reduction should be discussed with the Medical Monitor.

If doses >12 µg/kg/day are explored, consult with the Medical Monitor for potential reduced doses for subsequent cycles.

7.6 Treatment Discontinuation

7.6.1 Criteria for Treatment Discontinuation

SL-401 treatment may be discontinued for any of the following reasons:

- Patient withdrawal of consent
- Occurrence of unacceptable toxicity, including DLT
- SL-401 related anaphylaxis or Grade ≥ 3 hypersensitivity reaction
- Requirement for > 1 dose reduction unless there is evidence of MRD eradication or sustained AML remission (beyond Cycle 2), in which case additional dose reductions are permitted, however, these reductions must be discussed with the Medical Monitor and documented in the context of ongoing AML response.
- Disease recurrence/progression
- Intercurrent illness that prevents further administration of SL-401
- Patient non-compliance
- Occurrence of pregnancy
- Completion of 6 cycles of treatment. (The administration of additional cycles of SL-401 [beyond 6 cycles] may be considered in the setting of MRD eradication, sustained AML remission, or other evidence of sustained anti-leukemia benefit in the opinion of the Investigator. Administration of SL-401 beyond 6 cycles must be discussed with the Medical Monitor at which time the individual patient's potential risk/benefit of further treatment will be assessed).

- Investigator's decision

The reason for SL-401 discontinuation and the date of discontinuation should be recorded in the eCRF.

7.6.2 Procedures and Follow-up after Treatment Discontinuation

The evaluation during which the Investigator determines that SL-401 will be discontinued should be considered the End of Treatment Evaluation; all tests and procedures for the End of Treatment Evaluation are listed in [Table 6](#). In addition, patients should be followed for a minimum of 30 days after the last infusion of SL-401 for assessment of AEs (including potential new AEs and potential change/resolution of existing AEs).

If the patient is in CR/PR at the time of discontinuation, tumor assessments should continue to be performed as described in Section [8.11](#) until, in the judgment of the Investigator, there is evidence of relapsed or progressive disease. Beyond the End of Treatment Evaluation and 30-day follow up (safety/AE assessment), it is requested that subsequent follow-up occur approximately every 90 days for ascertainment of survival status.

If the patient discontinues SL-401 treatment and also withdraws consent for collection of future information, no further evaluations should be performed and no additional data should be collected as part of the study. The Sponsor will only retain and use any data collected before withdrawal of consent.

Please consult Section [6.4](#) for recommendations concerning ongoing follow-up of patients alive with or without evidence of disease progression at the time of Study Completion/assessment of primary and critical secondary endpoints.

8 Study Procedures

